7.5 Product Packaging and Handling

OpenBiome will package investigational and placebo FMP250 units in PET Corning bottles with HDPE screw-caps (pictured below). All units will be shipped by overnight carrier in dry ice inside a Styrofoam cooler with a WarmMarker temperature indicator attached to the lid. Upon arrival to the [name] laboratory, the package will be immediately checked for product tampering and temperature exposure. Each unit should be sealed and then stored promptly in a -20 or -80 Celsius degree freezer. The seal should not be broken unless the sample is going to be thawed the same day for delivery.

FMT Lower Delivery*250 mL microbiota preparation for delivery via colonoscopy, enema or sigmoidoscopy under medical supervision*

NOW® Foods packages each Psyllium Husk Powder, Organic product in a white plastic bottle with a sealed cap. The bottle is approximately 6.5 inches tall and 3.5 inches wide. Upon arrival to the [name] Laboratory, the package will be immediately checked for product tampering and accounted for by the *Psyllium Tracking Log* form.

7.6 Product Storage and Stability

Investigational and placebo FMP250 units must be stored in a freezer at all times until directly before use. The units are stable for up to 6 months at -20 degrees Celsius or 12 months at -80 degrees Celsius. Product stability is not compromised by freezer temperature shifts of up to five degrees Celsius.

NOW® Foods recommends their *Psyllium Husk Powder, Organic* product be stored in a dry and cool place after opening. We assume the same is recommended for its storage at WCMC, before its distribution to subjects.

7.7 Product Preparation

1. Thawing
 - a. All FMP250 units must be thawed prior to use by one of the following methods:
 - i. 1 hour in a 30-degree Celsius water bath
 - ii. 4.5 hours at room temperature
 - iii. 16 hours in a refrigerator
 - b. Thawed material must be homogenized by mixing for 10 seconds before delivery

Any leftover FMP250 material must never be reused or refrozen. It should be immediately disposed according to internal WCMC/NYPH protocol.

7.8 Dosing and Administration

7.8.1 FMP250

Prior to colonoscopy subjects will be asked to undergo bowel prep and to fast the night before the procedure. Additionally, subjects will be provided anti-diarrheal agent(s) 1-2 hours prior to the procedure to aid with retention of the fecal transfer, which ideally would be for up to four hours.

The study intervention will only be infused through the working channel of the instrument during colonoscopy at the day 0 screening visit if the clinician confirms the subject meets the endoscopy dependent inclusion criteria. A 250cc dosage of the investigational or placebo FMP250 will be delivered in aliquots of 60cc but we also recognize that some fecal material may be lost during the transfer. During the week 8 flexible sigmoidoscopy, subjects that were randomized into the placebo group will receive a 250cc dose of investigational FMP250 and subjects that were randomized into the investigational group will receive a 250cc dose of placebo FMP250.

Once the FMP250 has been thawed, it is stable for administration for up to 4 additional hours at room temperature or 8 hours refrigerated.

7.8.2 Psyllium

Subjects randomized into the psyllium fiber treatment group will receive two bottles of the *Psyllium Husk Powder, Organic* product to begin consuming three days prior to the day 0 colonoscopy. They will be asked to take one teaspoon (approximately 5 grams) of this fiber supplement twice a day until their week 8 clinic visit which will be approximately 59 days. The twice a day dosage is advised to be taken once in the morning (e.g. breakfast) and once in the night (e.g. dinner) to help with subject compliance.

NOW® Foods recommends a tablespoon of this product to be mixed in at least a cup of liquid to avoid the risk of choking.

7.8.3 Dosing Delays/Dose Modifications

Not Applicable.

7.9 General Concomitant Medication and Supportive Care Guidelines

All concomitant medications will be recorded and/or updated on subject medication log throughout the course of the study and saved in subject binder and REDCap.

7.10 Duration of Therapy and Criteria for Removal from Study

Subjects assigned to the investigational FMP250 treatment groups will receive the FMT once at the day 0 colonoscopy and will subsequently receive the placebo FMP250 at week 8 to minimize unblinding bias between FMT treatment arms. Subjects assigned to the placebo FMP250 will also

receive the investigational drug once at the week 8 flexible sigmoidoscopy. The therapy is not given over a cycle or extended period of time.

Subjects assigned to the psyllium fiber treatment groups will take the fiber supplement twice daily beginning three days prior to the colonoscopy until the week 8 follow-up clinic visit. Subjects who do not comply to the recommended dose will not be removed from the study, however, they may not be evaluable for scientific analysis for this treatment group. In the case that a subject cannot tolerate the fiber supplement due to uncomfortable side effects, we recommend they decrease the dose to one teaspoon a day for a week before discontinuing the supplement altogether. Any subject tolerating the advised psyllium dose for less than one week will not be considered in this intention to treat trial as tolerating intervention, however, they will still continue with the FMT intervention. Importantly, subjects will be considered evaluable for scientific analysis in the *Fiber + placebo or active FMT* treatment group if they take the psyllium dosage for at least one-week post-FMT procedure up until the 4-week post-FMT clinic evaluation.

Study Termination Guidelines: A subject's follow-up in the study will end after one of the following applies:

- Subject's voluntary withdrawal
- Subject lost to follow-up
- Subject death
- Completion of all scheduled study follow-up clinical visits and phone calls

7.11 Duration of Follow Up

Subjects will receive subsequent follow-up phone calls every 6 months for the following year after completion from study (in-clinic visits) or until death, whichever occurs first. Subjects removed from study for unacceptable adverse events will be followed by the treating clinician and/or principal investigator until resolution or stabilization of the adverse event.

7.12 Measures to Minimize Bias: Randomization and Blinding

Randomization Bias:

A series of randomized blocks of fixed size will be generated with a 1:1:1 allocation ratio. This will provide assurance that after a given block as completed subject enrollment, there will be the same number of subjects assigned to each of the three study arms. Only the statistician and the study coordinator will have access to the randomization list. The dedicated research coordinator will assign the randomization code from the list for each subsequently enrolled patient (i.e., the statistician will give the list that contains the randomized blocks only to the research assistant).

Unblinding Bias:

Clinicians are blinded while they assess the clinical response at week 8 and will be unblinded only once all clinical evaluations at week 8 have been conducted for all 135 study participants. This will reduce the risk of potential bias by the clinician as all treatment groups will receive treatment (blinded investigational or placebo FMP250) at week 8 by flexible sigmoidoscopy.

Unblinding in the case of emergency (i.e. anticipated or unanticipated serious adverse event) is up to the discretion of the treating physician, particularly if it is medically necessary to know what treatment assignment the subject received. However, it is advised that the treating physician

discuss with the principal investigator prior to breaking protocol. The study coordinator will not delay or refuse unblinding if knowledge of the investigational drug is imperative for emergency treatment. The study coordinator will then immediately notify the PI of unblinding and will document the reason in the subject's folder and/or eCRF.

7.13 Study Intervention/Follow-up Compliance

Adherence to the protocol can be assessed and verified from logs, such as eligibility checklists and standard operating procedures (SOPs), that will be created by study coordinators and confirmed by the treating clinician throughout the course of the intervention. These logs will be based on the schedule of events detailed in **Section 6.1, Table 1.** to ensure the subject's compliance and that all data collection is successfully completed and reviewed at each visit. These paper forms will be stored in each subject's study binder.

In our previous pilot study, we also utilized single colonoscopic delivery of FMP250 and did not experience any loss to follow up due to our short-term follow-up clinic evaluation at 4 weeks post-FMT. Therefore, we anticipate our loss to follow-up rate to remain consistent in this new clinical trial. Considering patients will be blinded up until all study subjects complete week 8 evaluations, we expect them to comply with our follow-up clinic visits because the subject would want to ensure they received the investigational drug. However, if a patient does not respond after three contact attempts (either phone call and/or e-mail) by the study coordinator they will be labeled as a lost to follow-up.

In regard to safety-phone calls at 6-months and 1-year, subjects will be contacted three times (either phone call and/or e-mail). Should subject fail to answer, the investigator or designee will mail a certified letter to the subject's last known mailing address in order to regain contact.

8. Study Intervention Discontinuation and Participant Discontinuation/Withdrawal

8.1 Discontinuation of Study Intervention

Discontinuation from receiving FMP250 does not mean discontinuation from the study, and remaining study procedures should be completed as indicated by the study protocol. If a clinically significant finding is identified (including, but not limited to changes from baseline) after enrollment, the investigator or qualified designee will determine if any change in participant management is needed. Any new clinically relevant finding will be reported as an adverse event (AE). Certain AE/SAEs may result in a safety review and may cause for the discontinuation of the study intervention. See **Section 15.2.** for details on halting rules.

Discontinuation of Psyllium Husk Powder, Organic during the approximately eight-week course does not translate to discontinuation from this study. Any subject tolerating the advised psyllium dose for less than one week will not be considered as tolerating intervention, however, they will still continue with the FMT intervention. Therefore, the remaining study procedures should be completed as indicated in the study protocol. Further details on what to do if a subject does not finish the complete fiber supplement course can be found in **Section 7.10.**

The data to be collected at the time of study intervention discontinuation will include the following:

- Reason for discontinuation (escalation of care, not feeling well, surgery, etc.)

- All follow-up evaluations (AE/SAE reporting via phone calls, clinic visits) detailed in **Section 13.**

8.2 Participant Discontinuation/Withdrawal from the Study

Subjects are free to withdraw from participation in the study at any time upon notification. However, if a subject decides to stop participating in the study we encourage them to speak with the research coordinator or investigator first.

An investigator may discontinue or withdraw a participant from the study for the following reasons:

- Pregnancy
- Significant study intervention non-compliance
- If any clinical adverse event (AE), laboratory abnormality, or other medical condition or situation occurs such that continued participation in the study would not be in the best interest of the participant
- Disease progression which requires discontinuation of the study intervention
- If the participant meets an exclusion criterion (either newly developed or not previously recognized) that precludes further study participation
- Participant lost to follow-up after several attempts to contact subject to schedule study visit.

Patients withdrawn because of SAEs, AEs or at the discretion of the physician will continue to receive treatment in accordance with current standard of care. Patients having AEs will be monitored with relevant clinical assessments, laboratory tests, imaging studies and procedures as determined by the treating physician.

The date and reason for participant discontinuation or withdrawal from the study will be recorded on an electronic Case Report Form (eCRF) created on REDCap. Subjects who sign the informed consent form and are randomized but do not receive the study intervention may be replaced. Subjects who sign the informed consent form, and are randomized and receive the study intervention, and subsequently withdraw, or are withdrawn or discontinued from the study, will not be replaced.

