4.5 Screen Failures

Screen failures are defined as participants who consent to participate in the clinical trial and have potentially been randomized into a treatment assignment but do not meet all inclusion criteria, specifically the endoscopy scoring for active disease at the day 0 standard of care colonoscopy. A minimal set of screen failure information is required to ensure transparent reporting of screen failure participants, to meet the Consolidated Standards of Reporting Trials (CONSORT) publishing requirements and to respond to queries from regulatory authorities. Minimal information includes demography, screen failure details, eligibility criteria, and any serious adverse event (SAE).

Individuals who do not meet the criteria for participation in this trial (screen failure) at the day 0 standard of care colonoscopy may be rescreened at a later time.

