6.1.2 Treatment Phase

Eligible subjects will be randomly assigned to one of the three (Placebo or Investigational FMP250 +/- Psyllium) treatment groups. A series of randomized blocks of fixed size will be generated with a 1:1:1 allocation ratio. This will provide assurance that after a given block has completed subject enrollment, there will be the same number of subjects assigned to each of the three study arms.

Treatment assignment will be done during the screening visit because participants randomized to receive fiber supplementation must be provided two psyllium bottles to begin consumption 3 days prior the colonoscopy.

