Considering analyses will be performed based on intent to treat, any subject in the FMT alone (no psyllium) or the FMT with psyllium intervention groups with missing primary endpoint data at week 8 will be labeled as failed treatment (no change in clinical response from baseline). Therefore, subjects with missing data will have their baseline Mayo score carried forward to remain the same for the week 8 primary endpoint. For primary efficacy analysis, the populations FMT + psyllium vs. FMT alone (no fiber) will be compared by the chi-square test (pair-wise group comparisons will also be performed). Those characteristics found to be clinically different between groups at baseline using significance criteria of $p < 0.05$ or known to be clinically important (e.g., in the event randomization provided insufficient balance between groups) will be incorporated into a multivariable logistic regression model of clinical response (i.e., binary outcome variable). This will facilitate estimating the independent effect of treatment group status on clinical response, after controlling for such factors, if any, that may differ between the two study arms at baseline. Sensitivity analyses for the primary endpoint will also be performed; in addition to carrying forward the baseline Mayo score for subjects with missing data at week 8, the minimum, median, and maximum Mayo score of subjects with available data at week 8 will be used (imputed) for subjects with missing data at week 8. Similarly, we will also explore multiple imputation techniques under varying assumptions of missingness (e.g., missing completely at random and missing at random). These multiple imputation techniques will rely on regression models to predict the missingness and missing values, and incorporate uncertainty through an iterative approach. For dealing with the possibility of data not missing at random, a worst-case analysis will be explored (i.e., missing data are replaced with the “worst” value under the not missing at random [non-ignorable] assumption). These sensitivity analyses will allow for an assessment of the consistency of the primary endpoint difference between groups under the varying assumptions for missing data at week 8.

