12.6.2 Evaluation of Response

All subjects included in the study will be assessed for response to treatment if they meet all inclusion and exclusion criteria, and then receive either placebo or investigational FMP250 treatment during the screening colonoscopy.

13. Adverse Event Reporting Requirements

Adverse event (AE) monitoring and reporting is a routine part of every clinical trial. The investigator will be required to provide appropriate information concerning any findings that suggest significant hazards, contraindications, side effects, or precautions pertinent to the safe use of the drug or device under investigation. Safety will be monitored by evaluation of adverse events reported by subjects or observed by investigators or research staff, as well as by other investigations such as clinical laboratory tests, x-rays, electrocardiographs, etc.

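### Section 12.1 claims intent to treat, but the rules on screen failure, replacement and response evaluation allow the analysed set to be fixed after subjects know their fibre assignment

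*Combined protocol and SAP*

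**What the plan says.** Five parts of the combined protocol and SAP bear on who enters the primary test.

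- **Section 12.1** sets the principle, "Considering analyses will be performed based on intent to treat", and the test: "For primary efficacy analysis, the populations FMT + psyllium vs. FMT alone (no fiber) will be compared by the chi-square test". Any subject in those two groups "with missing primary endpoint data at week 8 will be labeled as failed treatment".
- **Section 12.6.2** says subjects are assessed for response "if they meet all inclusion and exclusion criteria, and then receive either placebo or investigational FMP250 treatment during the screening colonoscopy".
- **Section 4.5** defines screen failures to include people who consent and "have potentially been randomized into a treatment assignment but do not meet all inclusion criteria", naming the day-0 endoscopy scoring in particular. Those who fail at the day-0 colonoscopy "may be rescreened at a later time".
- **Section 8.2** allows replacement: "Subjects who sign the informed consent form and are randomized but do not receive the study intervention may be replaced". Subjects who received the intervention and later leave are not replaced.
- **Section 6.1.2** gives the order of events: "Treatment assignment will be done during the screening visit because participants randomized to receive fiber supplementation must be provided two psyllium bottles". Section 6.1.1 starts the fibre on day -3. It describes randomisation as blinded to clinician and subject, but no placebo fibre appears anywhere.

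**The concern.** Leaving out randomised subjects who were never treated is acceptable when leaving cannot depend on the assignment. That is hard to assume here. The primary contrast is fibre against no fibre among subjects given active FMT, and fibre is the part of the assignment a subject can see. It is known from the screening visit, and one arm has taken it for three days before day 0.

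There are two routes by which loss before FMT could differ by arm. A subject may withdraw on learning the fibre assignment, or after starting the fibre. Day-0 eligibility (section 4.2) also depends on a total Mayo score of 4 to 10 and on a stool frequency or bleeding sub-score of at least 1. Section 2.4.2 says psyllium can firm stool and reduce bowel movements, so it may move those items.

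If such subjects fall outside the analysed set, a difference in who stayed can look like a fibre effect or hide one. Every sensitivity analysis in section 12.1 imputes missing week-8 scores. None of them would reveal the loss of people who are not counted as missing.

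**Working it through.** **1. The passages side by side.** Take a subject randomised to FMT plus psyllium who fails the day-0 criteria, or who withdraws on day -1.

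- Section 12.1 read literally: the subject belongs to the group, has no week-8 score and is a failure.
- Section 12.6.2: the subject received no FMP250 or placebo and is not assessed for response.
- Section 4.5: the day-0 failure is a screen failure and may be rescreened. The withdrawal is not covered.
- Section 8.2: either subject may be replaced, if the intervention means FMP250 or placebo.

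No section defines the intent-to-treat set, says whether a replaced subject stays in the denominator, or says whether a rescreened subject keeps the first assignment.

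**2. The plan's own figure.** Inputs from section 12.1: 55% v 27%, 45 per arm, two-sided 0.05, about 80% power.

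- Unpooled normal approximation: SE = √[(0.55×0.45 + 0.27×0.73)/45] = √(0.4446/45) = 0.0994. Then 0.28/0.0994 − 1.960 = 0.857, which gives 80.4% power.
- Pooled formula: 78.0%. Exact power of the uncorrected chi-square: 77.6%.

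The stated figure reproduces.

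**3. What selective loss could do with no fibre effect.** Assume a true rate of 27% in both arms, replacement back to 45 per arm, and that everyone lost would have been a non-responder. If a fraction q is lost, the rate among those treated is 0.27/(1 − q): 0.300 at q = 0.10 and 0.338 at q = 0.20. The error is the exact probability that the uncorrected two-sided chi-square rejects, summed over all binomial outcomes.

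| Loss, fibre v FMT alone | Treated rates | Two-sided error |
|---|---|---|
| none | 27.0% v 27.0% | 5.4% |
| 10% v 10% | 30.0% v 30.0% | 5.4% |
| 10% v 0% | 30.0% v 27.0% | 6.5% |
| 20% v 10% | 33.8% v 30.0% | 7.1% |
| 20% v 0% | 33.8% v 27.0% | 11.2% |

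The loss fractions are assumptions. Section 12.2 expects 15 of 150 (10%) to be screening failures or dropouts, but does not split them by arm or by whether they were already randomised. Because all losses are taken to be non-responders, each row is an upper-end case for its loss pattern in this direction.

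**4. What an all-randomised analysis would show.** Suppose 10% of each arm is lost after randomisation and counted as non-response. The planning rates become 0.55×0.9 = 49.5% and 0.27×0.9 = 24.3%. With 50 randomised per arm (150/3), power by the pooled formula is 75.0%, against 78.0% for 45 per arm with no loss.

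**The case against.** The strongest reply is that the sections can be reconciled and that arm-related selection is conjecture. Section 12.6.2 may say only who is assessed, leaving section 12.1 to count everyone else as a failure. Clinicians are stated to be blinded, and all subjects are masked to FMT. Psyllium is supplied only to subjects who meet the non-endoscopic inclusion criteria at screening (section 2.4.2), so some of the expected 15 losses would occur before fibre status is known. Reasons for withdrawal and screen-failure details are already collected.

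Much of this stands, and it rules out several stronger readings that a reader might infer.

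- *Everyone lost before FMT is replaced, rescreened and dropped.* Section 8.2 says such subjects may be replaced. Section 4.5 covers unmet inclusion criteria and offers rescreening to day-0 colonoscopy failures, not to voluntary withdrawals. Exclusion from the analysis rests on section 12.6.2 and conflicts with section 12.1.
- *Replacement is lopsided because psyllium is listed as a study intervention in section 7.1.* Section 7.8.1 uses the term for the product infused at colonoscopy, and section 12.6.2 ties evaluability to FMP250 or placebo in every arm. The wording merits clarification, but an unequal rule is not established.
- *Vacated randomisation slots are reused, or rescreened subjects draw again.* Section 7.12 assigns codes from the list as each patient enrols. A second draw is inferred only from silence.

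Two things survive. A reading in which untreated subjects count as failures sits badly with calling some of them screen failures and replacing them. And blinded clinicians do not prevent withdrawal by a subject who knows the fibre assignment, or a change in the symptom items that decide eligibility.

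**Conclusion.** The plan is wrong as written in one respect: it states intent to treat but contains rules that point to a treated-only set, and nothing reconciles them. The discrepancy matters more than usual because the set would be fixed after subjects know the factor under test and after one arm has begun it.

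A reader might go further and conclude that the primary comparison is biased, or that its error is about 11%. The documents do not support either. Differential loss is possible, not shown, and equal 10% non-responder loss leaves the error at 5.4%. Applying the whole 10% planning figure to the fibre arm alone, all as non-responders, gives only 6.5%. The 11.2% needs an assumed 20% loss in one arm and none in the other.

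**What to change.** 1. Reconcile sections 4.5, 8.2, 12.1 and 12.6.2. Call the treated set modified intent to treat. Add a sensitivity analysis of all randomised subjects by first assignment, with every untreated subject counted as a non-responder. Show it both including and excluding day-0 eligibility failures, because the total Mayo, stool frequency and bleeding items that decide eligibility may respond to psyllium.
2. Report losses before FMT, day-0 failures and their reasons by arm. The reasons are already to be recorded; the split by arm is what is missing.
3. State in section 4.5 that a rescreened subject who was already randomised keeps the first assignment and is counted once. Such a subject still decides on re-entry knowing the fibre status, so the by-arm report should show re-entries too.
4. Clarify in section 8.2 that receiving the study intervention means the day-0 FMP250 or placebo in every arm, in line with sections 7.8.1 and 12.6.2.

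The cost is wording and one extra analysis, with no added patients or procedures. The all-randomised analysis will show somewhat lower response rates (49.5% v 24.3% in the example above) and slightly less power. As a sensitivity analysis it does not require a new sample size. The definitions should be settled before unblinding.
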